# RESEARCH PROJECT: Development of an assessment protocol sensitive to the cognitive processes necessary for driving after stroke

# 21st November 2022

# OBJECTIVES

## GENERAL OBJECTIVE

TO DEVELOP AN ASSESSMENT PROTOCOL BASED ON ANALYSIS OF VARIABLES THAT MAY PREDICT SAFE "FITNESS TO DRIVE" ("Fitness to drive") IN PATIENTS WITH STROKE

## SPECIFIC OBJECTIVES

- 1. SELECTION AND CREATION OF A BATTERY OF NON-DRIVING TESTS: COGNITIVE TESTS, PERSONALITY TESTS, RISK ESTIMATION AND ASSESSMENT OF DRIVING STYLES THAT MAY PREDICT SAFE "FITNESS TO DRIVE" ("Fitness to drive") IN PATIENTS WITH STROKE:
- Creation of the driving planning test: Evaluation of driving planning on Map (COMAP)
- Cross-cultural adaptation and validation in Spanish population of Stroke Driver's Screnning Assessment (SDSA).
- Cognitive tests to predict driving performance and identify cognitive deficits, including general cognitive tests, attentional tests, speed of processing, visual memory and executive functions.
- Personality and Risk Estimation Tests: Risk Estimation Test: DOSPERT-i.e. Recreational Risk Perception and Sensitivity to Reward and Punishment Test -SPSRQ-20 SR\* - Sensitivity to Reward.
- Assessment of driving styles: Multidimensional Driving Styles (MDSI), selfreported driving styles questionnaire: Maladaptive vs. Adaptive (Cautious) Padilla, Castro, Doncel, Taubman-Ben-Ari, 2019).
- PERFORMANCE-BASED TESTS ON HAZARD PERCEPTION AND RISK ESTIMATION, using recordings of naturalistic driving situations (Castro et al., 2014; Ventsislavova et al., 2016).
- 2. CREATION OF A DRIVING SIMULATOR DRIVING PERFORMANCE ASSESSMENT TEST. The test called EDEC (Performance Evaluation of Driving) will be designed through a panel of experts (content validity) and the psychometric properties will be analysed.

# HYPOTHESIS

Based on the literature on the subject of driving after stroke, our hypothesis is that this selection of non-driving, performance-based tests in conjunction with the two newly created tests: COMAP and EDEC will be crucial in establishing a decision as to whether a patient with stroke, who previously had a driving licence, is able to drive safely.

In relation to the SDSA battery, our hypothesis is that the translated and cross-culturally adapted version will be a tool with good reliability and validity.

# METHODOLOGY

## STUDY DESIGN

Validation of an assessment protocol for safe driving ability in stroke patients, analysing the ability of selected tests designed to predict safe driving in on-road tests.

PARTICIPANTS AND INCLUSION CRITERIA

For the study, there will be 2 groups: (participants will sign the informed consent to participate in the study).

Patient group: 50 adults (between 18 years and 70 years) in chronic phase of stroke (>6 months since stroke) who have a driving licence and have been driving in the three months prior to stroke.

Exclusion criteria:

- Patients must have medical clearance to participate in the study (indicating that they are medically stable to participate in the study, regardless of whether they can drive or not).
- Patients will be excluded if they have a stroke score below 24 on the Mini Mental State Examination, epileptic seizures, visual impairments (uncorrected visual acuity with glasses, diplopia, severe campimetric or visual field deficits, etc.), attentional hemineglect syndrome, severe motor/balance disturbances and people who don't know/can read.
- They will be required to be able to move independently in a standing position, even if they need the help of assistive devices to do so.

Control group: 50 adults, matched in age, healthy, matched in driving experience (number of years of driving licence, kilometres driven in the last year, frequency of driving -daily, weekly, monthly, monthly, yearly, etc...), age, sex and educational level with the following characteristics age, sex and educational level with the group of people with stroke with a valid driving licence.

## RECRUITMENT

Patients will be recruited from the Regional University Hospital of Malaga and the Hospital of Torremolinos (Malaga), both hospitals provide care for most of the stroke patients in the province of Malaga from the public system. In addition, SINERGIA AISSE neurorehabilitation center and acquired brain injured association ADACEMA (Málaga) and ACTIVANEURO (Málaga).

## VARIABLES

Variable	Туре	Value
Age	Continuous quantitative	Years
Sex	Qualitative dichotomous	Male / Female
Marital status	Qualitative categorical	Single/ Married/Widowed/ Single/ Married/Widowed/ Single/ Married/Widowed/ Single/ Married/Widowed Divorced
Educational level	Qualitative categorical	Primary Education Secondary Education Vocational training University students
Radiological report of brain damage	Qualitative	
Localisation of brain damage	Qualitative categorical	Right/Left Frontal/parietal/temporal/occipital
Date brain damage	Continuous quantitative	Years and months
Rehabilitation time	Continuous quantitative	Years and months
Years with driving licence	Continuous quantitative	Years and months
Kilometres travelled in the last year	Continuous quantitative	Approximate number of kilometres
Driving frequency	Qualitative categorical	daily, weekly, monthly, monthly, yearly
Mini Mental State Examination	Continuous quantitative	Total score: 0-30
VOSP	Continuous quantitative	Sub-test scores: - Shape detection: 0-20 - Test 3: Object decision: 0-20 - Test 4: Progressive silhouettes: 1- - Test 5: Position discrimination:0-20 - Test 7: Locating numbers:0-10
The Used Field of View Test (UFOV)	Continuous quantitative	Time (milliseconds) Stimulus identification:16ms-500ms Divided attention:16ms-500ms Selective Attention: 43ms-500 ms Total subtests 1-3: 86ms-1500ms
Trail Making Test Part A and B	Continuous quantitative	Total score. Errors and time taken (seconds)
"Continuous Performance Test (CPT).	Continuous quantitative	False positives Omissions Reaction time
PASAT	Continuous quantitative	Errors: 0-60 Realisation time
Five-Digit Test.	Continuous quantitative	6 variables (both scalar and percentile scores)
Ineco Frontal Screening	Continuous quantitative	Total score 0-30
Iowa Gambling Test	Continuous quantitative	Total score for each block of 20 cards (5 blocks). The task score is obtained by subtracting the total number of choices of the disadvantageous decks from the number of choices of the advantageous decks.
Weekly. Weekly Calendar Planning Activity (WCPA).	Continuous quantitative	Planning time     Execution time     Correct quotations     Errors

		
 
Strategies used
 

### Tests for inclusion/exclusion of patients

- Boston test (reading comprehension): The person has to read 4 sentences and determine the correct option to finish the sentence (4 options).
- Test Snellen: is a visual test carried out on the patient to evaluate their eye capacity and to see if there is any alteration that may be hindering their vision, thus measuring their visual acuity.
- Time up and go: is a test used to assess a person's mobility and requires both static and dynamic balance. It uses the time that a person takes to rise from a chair, walk three meters, turn around 180 degrees, walk back to the chair, and sit down while turning 180 degrees.
- 5 Sit to Stand Test: measures one aspect of transfer skill. The test provides a method to quantify functional lower extremity strength and/or identify movement strategies a patient uses to complete transitional movements.
- Evaluation of simulator performance possibility and pain.

### PROCEDURE

The occupational therapists will contact those responsible for the recruitment centres to indicate the inclusion/exclusion criteria for participation in the present study. Participants who meet the criteria will be informed about the study and if they voluntarily agree to participate, they will be asked to sign a consent form authorising them to give their telephone number to the researchers. The researchers will provide more detailed information about the study by telephone, and if the person agrees, an appointment will be made to carry out the assessment.

The total duration of the evaluation protocol will be approximately 7 hours, although it depends on the participant's performance. It will be divided between the sessions required by the person, depending on their abilities, but will be at least 3 sessions.

In the first session, the participant is again informed about the project and encouraged to ask any questions he/she may have. The person will be offered an information sheet and the participant will have to sign the informed consent form. The assessment will then begin, asking questions about socio-demographic data, collecting information about the injury and data in relation to driving. Subsequently, the list of off-road tests indicated in the protocol will be administered. In all sessions, approximately 30 minutes of driving time will be spent on the driving simulator in order to mitigate possible non-serious adverse effects such as dizziness. Once the off-road tests have been completed, the in-car simulator test will be carried out, followed by the on-road test. For the on-road test, in all patients, a 30-minute session will be devoted to adapt to that driving

mode. The on-road test will be carried out in the presence of 3 people: a driving school teacher and 2 researchers.

At the end of the on-road test, general feedback will be given by the driving instructor.

# 21st November 2022

# PLAN ANALYSES

# ANALYSIS TO IDENTIFY THE TESTS OR SET OF TESTS THAT SIGNIFICANTLY PREDICT THE ON-ROAD TEST.

- Linear regression models will be used to assess the predictive ability of the different tests on the performance measure in the on-road test - response variable.
- Furthermore, participants will be divided into those who are fit to drive, those who are doubtful and those who are unfit based on the on-road test. Based on this, a discriminant function analysis will be performed.
- The diagnostic accuracy of the tests included in the protocol will be performed for the identification of fit/unfit/borderline patients for the on-road test through a receiver operating characteristic (ROC) curve analysis, where larger areas under the curve (AUC) indicate better diagnostic accuracy. The optimal cut-off points will be determined by the Youden index formula, where the highest Youden index indicates maximisation of sensitivity and specificity. For each cut-off point we will calculate sensitivity (the probability that participants with skills can get a pass in the On-Road driving test) and specificity (the probability that participants without skills will get a fail in the On-Road driving test).

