## **VALIDATION OF COMAP AND THE SPANISH VERSION OF SDSA**

The validation of the COMAP, as a newly created scale, will be carried out by calculating the following psychometric properties:

Convergent validity, through correlation analysis.

- Semantic memory: Road Sign Recognition Test. SDSA\*.
- Selective attention: UFOV, Trail Making test.
- Working memory: PASAT
- Planning, inhibition, working memory, mental flexibility and strategy use: Spanish Weekly Calendar Planning Activity\*.

Incremental Functional Validity: On-road driving report, through regression analysis. External Validity: Comparison with parametric (Student's t-test) or non-parametric (Mann Whitney U) tests between Stroke/unaffected persons.

Reliability: Crombach's alpha

Sensitivity and specificity: ROC Curve

\*Only for COMAP validation.

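### Cut-offs are chosen by the highest Youden index and their accuracy is calculated on the same people, with no internal validation, so the reported sensitivity and specificity will on average be too high

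*SAP*

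**What the plan says.** The first analysis section of the SAP is headed "ANALYSIS TO IDENTIFY THE TESTS OR SET OF TESTS THAT SIGNIFICANTLY PREDICT THE ON-ROAD TEST". It plans linear regression, a discriminant function analysis on three on-road classes, and ROC analysis. On the last it says: "The diagnostic accuracy of the tests included in the protocol will be performed". The cut-off rule is: "The optimal cut-off points will be determined by the Youden index formula, where the highest Youden index indicates maximisation of sensitivity and specificity". The next sentence begins: "For each cut-off point we will calculate sensitivity".

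The two later SAP sections, on COMAP with the Spanish SDSA and on EDEC, each plan "Sensitivity and specificity: ROC Curve" without naming a cut-off rule.

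The Protocol (Study design) describes the project as "Validation of an assessment protocol for safe driving ability in stroke patients". It enrols one patient group, "50 adults (between 18 years and 70 years) in chronic phase of stroke", and 50 matched healthy controls. The SAP's ROC sentence speaks of patients, while the neighbouring sentences speak of participants, so n is 50 or 100.

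No split sample, cross-validation, bootstrap or external sample appears in the SAP text available. The validation listed for COMAP, SDSA and EDEC is psychometric: convergent validity, incremental validity, a stroke/unaffected comparison and Cronbach's alpha. None of these corrects for having chosen a cut-off on the data.

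**The concern.** A cut-off placed where the sample's J is highest is partly fitted to chance features of that sample. Measuring accuracy at that point on the same people credits the test with the chance part as well.

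Cut-offs with their sensitivity and specificity are a main product of this analysis. The Protocol's hypothesis expects the tests to matter greatly in deciding whether a patient can drive safely. Overstated specificity understates the share of unfit drivers whom the test would call fit. Nothing in the SAP labels the cut-offs as provisional or warns that their accuracy is apparent only.

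**Working it through.** **Direction of the bias.** Let Ĵ(c) be the sample value of J at cut-off c, and ĉ the cut-off that maximises it. For each fixed c, Ĵ(c) is unbiased for the true J(c). Hence E[max Ĵ(c)] ≥ max J(c) ≥ E[J(ĉ)]. Apparent J is too high on average, and no assumed figure is needed to show it. For sensitivity and specificity taken separately, the overstatement is on average and appeared in every setting simulated. The AUC of one pre-named test with its direction fixed involves no maximisation and is unbiased.

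**Inputs.** From the documents: n=50 or 100, and the cut-off rule. The documents give no accuracy target, sample-size derivation, class split or test accuracy, so there is no figure of the plan's own to reproduce. The rest is assumed:
- Scores are normal with equal variance, and the fit and unfit means differ by d standard deviations.
- The three on-road classes have been reduced to two; the SAP does not say how.
- Fit/unfit splits are 25/25 or 35/15 (n=50), and 50/50 or 70/30 (n=100).
- Sensitivity is the share of on-road passes the test calls fit, and specificity the share of on-road fails it flags. The SAP's own wording, "specificity (the probability that participants without skills will get a fail in the On-Road driving test", can be read the other way round.

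**Formulas.** Call fit if the score exceeds c, with the unfit mean at 0 and the fit mean at d. True sensitivity = 1 - Φ(c - d) and true specificity = Φ(c). True AUC = Φ(d/√2). The best attainable J is 2Φ(d/2) - 1. For d=0.8 these last two are Φ(0.566) = 0.71 and 2 × 0.655 - 1 = 0.31.

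**One pre-named test, continuous score (6000 simulated studies per setting).** Apparent J is measured on the sample; true J is the model value at the cut-off actually chosen.

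| d | n=50: apparent / true J | n=100: apparent / true J |
|---|---|---|
| 0.5 | 0.32-0.33 / 0.17 | 0.28-0.29 / 0.18 |
| 0.8 | 0.41-0.43 / 0.28 | 0.38-0.39 / 0.29 |
| 1.2 | 0.54-0.55 / 0.42 | 0.51-0.52 / 0.43 |

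Before rounding, the excess is about 0.12-0.16 at n=50 and 0.08-0.11 at n=100. At d=0.8 the mean apparent AUC is 0.71 against a true 0.71.

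**Coarse scores.** The Protocol's variables table includes short integer scores, such as COMAP signal knowledge (0-4, 5 levels) and danger prediction (0-10, 11 levels). With so few possible cut-offs there is less to over-fit. Binning the d=0.8 model into 5 to 11 equal-width levels gives an excess J of about 0.06-0.10 at n=50 and 0.04-0.06 at n=100.

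**In terms of drivers (continuous score, d=0.8, 35 fit/15 unfit).** Mean specificity is 0.736 apparent and 0.633 true. The reported share of unfit drivers passed by the test is 1 - 0.736 = 26%; the true share is 1 - 0.633 = 37%. With 5 to 11 levels the gap is about 5-7 percentage points.

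**Intervals.** Take the Wald interval, apparent J ± 1.96 × √[se(1-se)/n_fit + sp(1-sp)/n_unfit]. For continuous scores at d=0.8 it contains the true J in about 78% of runs at 35/15 and 81-84% at the other splits, against a nominal 95%. Nearly all misses are in the too-favourable direction.

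**The case against.** Four points can be made for the plan.

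- **This is development work.** The general objective is to develop a protocol, and the hypothesis is not a licensing rule. That stands, and it lowers the severity. It does not remove the need for honest accuracy figures, because the design is also called a validation and the cut-offs carry no caveat.
- **Continuous scores exaggerate the bias for many listed tests.** This stands; the coarse-score figures above are the answer to it. Timed measures such as UFOV and Trail Making stay close to the continuous figures.
- **Corrected figures are noisy at n=50.** This stands too. For one d=0.8 test at 35/15, the root-mean-square error of J falls only from 0.19 (apparent) to 0.15 (cross-validated), and in a single data set the corrected value can lie further from the truth. The case for correction is removal of a known bias.
- **The SAP may simply report every test.** The ROC sentence reads that way. The one-test bias applies to each test regardless.

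A reader might infer more: that the best of some 62 scores will be kept and its AUC badly inflated. With one useful score (d=0.8) among 62, n=50 and the highest AUC kept, simulation gives AUC 0.74-0.76 against 0.60-0.65. The documents do not support this as a prediction. The section heading announces a search, but no passage ranks tests by AUC. The score count is also uncertain. The specific objectives name only the recreational part of DOSPERT and a two-way grouping of driving styles, and the Mini Mental State Examination is an entry criterion. Counting these as 1, 2 and 0 instead of 6, 6 and 1 gives 62 - 5 - 4 - 1 = 52. No multi-test set was simulated.

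**Conclusion.** The concern holds, as something that should be fixed and is cheap to fix. Followed as written, the SAP reports J, and on average sensitivity and specificity, that are too favourable even for a single test fixed in advance. The direction follows from the rule itself. The sizes rest on normal scores and assumed splits: excess J of about 0.12-0.16 (n=50) or 0.08-0.11 (n=100) for continuous scores with d=0.5-1.2, and roughly half to two-thirds of the corresponding d=0.8 values for 5- to 11-level scores. The n=100 figures also treat patients and controls as one population.

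If a test or set is picked by its result, its AUC is overstated too and the excess in J is larger. How much larger depends on the number of candidates and the selection rule, neither of which the SAP states.

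Two stronger readings should be resisted. AUCs are not biased across the board: that of a pre-named test is sound. Nor is the study compromised: the correction uses the same data, and nothing in recruitment or measurement is lost.

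**What to change.** Amend the SAP's prediction analysis, and the ROC lines for COMAP, SDSA and EDEC if the same cut-off rule is used there:

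1. Before on-road results are seen, name the candidate score or scores for each test and the rule for selecting a test or set.
2. Keep the planned regression, discriminant and ROC analyses, but repeat any test selection, model fitting and cut-off choice inside an internal validation. Repeated cross-validation stratified by on-road class is suitable; so is an optimism bootstrap, if its remaining bias is stated. For one d=0.8 test at 35/15, mean J was 0.43 apparent, 0.27 cross-validated, 0.33 bootstrap-corrected and 0.28 true.
3. Report corrected AUC, sensitivity and specificity, with intervals described as approximate, beside the apparent values.
4. Report every named test, and describe the cut-offs as derived, pending validation in new patients.

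The cost is SAP wording and computing time; no patients or procedures are added. Headline accuracy will be lower. Corrected figures will be imprecise at n=50: in the same example, cross-validated J runs from 0.02 to 0.53 (5th to 95th percentile).

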## **VALIDATION OF COMAP AND THE SPANISH VERSION OF SDSA**

The validation of the COMAP, as a newly created scale, will be carried out by calculating the following psychometric properties:

Convergent validity, through correlation analysis.

- Semantic memory: Road Sign Recognition Test. SDSA\*.
- Selective attention: UFOV, Trail Making test.
- Working memory: PASAT
- Planning, inhibition, working memory, mental flexibility and strategy use: Spanish Weekly Calendar Planning Activity\*.

Incremental Functional Validity: On-road driving report, through regression analysis. External Validity: Comparison with parametric (Student's t-test) or non-parametric (Mann Whitney U) tests between Stroke/unaffected persons.

Reliability: Crombach's alpha

Sensitivity and specificity: ROC Curve

\*Only for COMAP validation.

### **CREATION and VALIDATION EDEC**

#### **CREATION**

Phase 1. Initially, the working team composed of all the researchers of this project will meet to elaborate a first version of the driving assessment test with the simulator. The starting point will be the work published on different scales validated in other languages and contexts: P-Drive (Patomella, Tham, Johansson & Kottorp, 2010; Patomella & Bundy, 2015). Test ride for investigating practical fitness to drive (TRIP) (Test to investigate practical fitness to drive) Driving Performance Inventory (DPI) (Lew et al., 2005).

Phase 2. A panel of experts will be formed using the DELPHI technique with the aim of achieving a reliable consensus among the opinions of a group of experts, through the sending of the draft assessment tool initially proposed by the working team, which will be answered anonymously. Objective to meet content validity.

Initially, the experts will be informed about the features of the DriveSiM simulator, as well as a possible route to be created for the test. In this sense, the experts will access a virtual platform where they will independently state their degree of agreement with the proposed items of the assessment tool. The degree of agreement will be established with a Likert-type scale (from 1 to 5) and, in addition, a space will be included where they will be able to make their comments freely, which will be considered a posteriori by the work team and will be used for the following rounds of consultation.

After each round, the working group will meet to resubmit a new questionnaire based on the results of the first round, in order to be re-evaluated by the expert committee, so that they can reconsider their answers, aided by the information received from the other experts.

The criteria for reaching a consensus will be a minimum of 2 rounds, at least 75% of the group of experts must agree or strongly agree on each item and an Interquartile Range / each item of less than 3 points.

The committee of experts will be composed of at least 7 persons, among them

- Occupational therapists in the field of neurology who are familiar with the potential and limitations of stroke patients.
- Professionals in the field of rehabilitation (occupational therapists among others) who have experience in the rehabilitation of driving in people with stroke.)
- Professionals in the field of driving in general.
- Scientists whose lines of research are focused on driving.

Phase 3. Test design. Once the measuring instrument has been designed and agreed upon by the team of experts, all the final assessment items of the new tool will be collected in writing.

